10.4 STATISTICAL ANALYSES

10.4.1 General Approach

This is a phase I study. There are two arms to this study for 1) patients with prior brachytherapy as a component of their treatment for prostate cancer, and 2) patients with prior EBRT without brachytherapy. Arms are enrolled and escalated separately. Groups of 3-6 patients are evaluated at each dose level. The dose level on which 2 patients experience unacceptable toxicity is considered to have exceeded the MTD. The next lower dose level on which no more than 1/6 patients experience unacceptable toxicity is considered the MTD for each arm of the study.

10.4.2 Analysis of the Primary Endpoint

The primary endpoint will be to define the MTD of this approach.

10.4.3 Analysis of the Secondary Endpoints

- Define the dose-limiting toxicities and toxicity profile of image-guided, focally dose escalated prostate SBRT in patients previously treated with radiotherapy: DLTs will be reported descriptively.
- Describe the rate of PSA control (bPFS, PSA < 2 ng/dL above post SBRT nadir) at 1 and 2 years after treatment with focally dose escalated SBRT for locally recurrent prostate cancer after irradiation: bPFS will be estimated by the Kaplan-Meier survival analysis and effects of clinical variables on bPFS will be assessed by the Cox proportional hazards model.
- Describe the effects of focally dose escalated prostate SBRT on patient reported outcomes (SHIM, AUA Symptom Index, EPIC-26) in patients previously treated with radiotherapy. The quality of life scores will be summarized at baseline and for each visit. Linear mixed effects model will be used to model quality of life scores at baseline and during and after treatment in which random intercept and random slope are used to account for patient-specific trajectory of quality of life scores. Changes of quality of life scores during and after treatment will be calculated from the estimated linear mixed effect model.
- Evaluate 18F-DCFPyL imaging as a method to detect locally recurrent prostate cancer after radiation. The sensitivity and specificity of DCFPyL for detecting locally recurrent prostate cancer (at baseline) will be reported using biopsy as the gold standard.

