SBRT has been investigated as a method to salvage patients with biochemical recurrence and documented local recurrence after radiotherapy for prostate cancer, but has only been reported in a single series (22). This approach takes advantage of the capacity for highly conformal therapy to minimize dose to surrounding structures while delivering a relatively homogenous dose compared to brachytherapy. Thus, areas of high dose to urethra and other structures are limited at the cost of increased low to moderate dose to surrounding rectum and bladder. In this series of 29 patients, SBRT was delivered to the prostate gland to a dose of 34 Gy in 5 fractions. In this series, dose was escalated to the peripheral zone, presumably to cover areas at “high risk” of recurrence, although the actual area of recurrence was not evaluated or escalated. The goal of this escalation as a prescribed dose of 42 Gy. Fourteen of these patients had residual toxicity from prior radiation treatments prior to receiving SBRT, and received a prior median radiation dose of 73.8Gy (range 68.4 Gy-81 Gy). Following SBRT treatment, these patients had a 2-year biochemical progression free survival (bPFS) of 82% using the Phoenix criteria. In regard to toxicity, 3 of the 29 patients developed late grade 2 genitourinary (GU) toxicity and one patient developed acute and late grade 3 GU toxicity (urethral obstruction with a suprapubic catheter and hemorrhagic cystitis). In addition, one patient required cystoprostatectomy for grade 4 hemorrhagic cystitis. Thus, the rates of GU toxicity for the 29 patients were 18% \geq Grade 2 GU toxicity and 7% \geq Grade 3 toxicity.

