10.2 SAMPLE SIZE DETERMINATION

Initially, the planned sample size is a minimum of 4 evaluable patients (2 per arm) and a maximum of 48 evaluable patients (24 evaluable patients maximum per arm). As of amendment version dates 04/13/2021 and 10/12/2021, determination has been made not to escalate either arm to dose level 3. Accordingly, a maximum of 42 evaluable patients may be enrolled (21 evaluable patients maximum per arm). Estimates for sample size are based on the assumption that all dose levels will accrue a maximum of patients, thus sample size is likely over-estimated. We do not anticipate drop out during treatment or follow-up, however that remains a possibility. We anticipate drop out would be minimal as we tend to accrue these patients from mainly the local area. To allow for a small number of patients who drop out or are not evaluable, we will set the accrual ceiling at 46.

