10.4.5 Sub-Group Analyses

The primary endpoint is based on toxicity at a dose level. Only 3-6 patients will be included per dose level except for the expansion cohort. Thus, it is not feasible to include sub-group analyses.

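### The Cox analysis of clinical variables on bPFS would rest on about 6 to 10 events, with no limit on the covariates, no exploratory label and no method suited to sparse events

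*Combined protocol and SAP*

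**What the plan says.** Section 10.4.3 estimates bPFS by Kaplan-Meier and adds that "effects of clinical variables on bPFS will be assessed by the Cox proportional hazards model". It does not name the variables, say how many there will be, say whether they enter singly or together, or give an expected event count. The sentence stands among the secondary analyses, not in the exploratory list of 10.4.7.

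Section 10.2 sets the current size: "a maximum of 42 evaluable patients may be enrolled (21 evaluable patients maximum per arm", reduced from "a maximum of 48 evaluable patients (24 evaluable patients maximum per arm". It adds, "thus sample size is likely over-estimated". To allow for drop-out, "we will set the accrual ceiling at 46".

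Two reference rates are given for bPFS. In the SBRT salvage series of 29 patients (section 1.2.1), "these patients had a 2-year biochemical progression free survival (bPFS) of 82% using the Phoenix criteria". Section 10.1 hypothesises a result that compares favourably with 75% after brachytherapy and attaches no time point to that figure. PSA is followed for two years (section 3.5). Under section 6.3.3 an event is PSA progression or death, and men recently on androgen deprivation are not evaluable for bPFS until testosterone recovers.

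**The concern.** A Cox model draws its information from events, not patients. A small salvage cohort with good expected control and two years of follow-up will yield few of them. Two problems follow. First, any hazard ratio will be very imprecise. Second, if every event falls on one side of a categorical covariate, the partial likelihood has no finite maximum: the estimate runs off to infinity, and the standard error and Wald interval carry no information.

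Because the covariates are not fixed, they could be chosen after the data are seen. A large hazard ratio produced by sparse data would then be reported as a secondary result rather than as a hypothesis. At stake is how the bPFS findings are interpreted, not any dose or safety decision.

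**Working it through.** **Sample size.** Under Table 3 (section 3.1.2), each dose level takes up to 6 patients and the recommended dose may take 6 more. With three levels, 3 × 6 + 6 = 24 per arm and 48 in total, which reproduces the initial maximum. With two levels, the same rule gives 2 × 6 + 6 = 18 per arm and 36 in total; the stated 42 is not reproduced. I use 42 as stated and 36 as a lower case.

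**Expected events by 2 years**, N × (1 − bPFS), over both arms:

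| N | bPFS 82% | bPFS 75% |
|---|---|---|
| 42 | 42 × 0.18 = 7.6 | 42 × 0.25 = 10.5 |
| 36 | 36 × 0.18 = 6.5 | 36 × 0.25 = 9.0 |

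Using 75% as a 2-year rate is an assumption. The brachytherapy series in section 1.2.1 report 65% to 85% at 5 years. Even 65% would give only 42 × 0.35 = 14.7 events. The exclusion of men whose testosterone is suppressed pushes the count down.

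**Precision for one binary covariate.** With d events and a fraction a of patients in one category, se(log HR) ≈ 1/√(d·a·(1 − a)). For a = 0.5 this is 2/√d, and the 95% interval multiplies or divides the hazard ratio by exp(1.96 × 2/√d). The two-sided 95% level is my assumption.

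- d = 6: exp(3.92/2.449) = 4.95
- d = 8: exp(3.92/2.828) = 4.00
- d = 10: exp(3.92/3.162) = 3.45

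**Chance that a category has no events**, with no true effect. For a category holding 20% of patients this is about 0.8^d:

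- d = 6: 0.8^6 = 0.26
- d = 8: 0.8^8 = 0.17
- d = 10: 0.8^10 = 0.11

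The same chance can be averaged over the number of events. With event probability q and category prevalence p, the probability that one side of the split has no events is (1 − pq)^N + (1 − (1 − p)q)^N. Prevalences are assumed, since the plan names no variables.

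| Setting | p = 0.50 | p = 0.35 | p = 0.20 |
|---|---|---|---|
| N = 42, bPFS 75% | 1% | 2% | 12% |
| N = 42, bPFS 82% | 4% | 7% | 22% |
| N = 36, bPFS 82% | 7% | 11% | 27% |

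Simulated null Cox fits (N = 42, exponential times, censoring at 24 months, bPFS 82%) gave matching rates of infinite estimates: 4%, 7% and 22% at the three prevalences. For a continuous covariate the rate was 0%. The failure is therefore specific to sparse categories; the imprecision is general.

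**The case against.** The best defence is that the objective in section 1.1.2 is to describe bPFS, which Kaplan-Meier does. No covariate hypothesis, error rate or power is claimed, so a phase I trial should not be faulted for lacking power to find prognostic factors. That stands, and I make no power argument. It is also true that the sentence in 10.4.3 does not rule out fitting covariates one at a time or with a penalty, and that a diverging fit shows itself through an enormous standard error. In simulated null fits with finite estimates, a Wald test at 1.96 rejected in 4.5% to 5% for a continuous covariate and 1% to 3% for a binary one, so per-variable false positives are not inflated.

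Four stronger readings are tempting and are not supported.

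- **That Cox regression does not work at this event count.** For a balanced binary covariate, infinite estimates are uncommon (1% to 7% in the table above); for a continuous one there were none in simulation. PSA at entry and time since radiotherapy, both plausible candidates, are continuous.
- **That 10.4.3 contradicts 10.4.5.** Section 10.4.5 does conclude, "Thus, it is not feasible to include sub-group analyses". Its reason is the primary toxicity endpoint: "Only 3-6 patients will be included per dose level except for the expansion cohort". The Cox model concerns a secondary endpoint and can pool dose levels and arms, so the two sections are compatible.
- **That some fixed share of fits, such as a quarter, would give an extreme hazard ratio.** Any such figure depends on the number and prevalence of the covariates, which the documents do not give.
- **That the absence of recurrence reported in section 1.2.5 foretells event-free groups.** Those are early 2021 observations, with only five men in Arm 2 having completed treatment. They say little about events at 24 months.

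What the defence leaves untouched is that 10.4.3 also permits many covariates, sparse categories and ordinary partial likelihood, with no exploratory label.

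**Conclusion.** The concern holds as a matter of specification and of method for sparse data. About 8 to 10 events are expected at 42 patients, and about 6.5 at 36 patients with 82% bPFS. A balanced binary covariate would have a 95% interval of the hazard ratio multiplied or divided by roughly 3.5 to 5. A category holding 20% of patients would have no events in 11% to 26% of trials under no effect, and ordinary Cox regression then returns no usable estimate. Continuous and balanced covariates would be imprecise but usually estimable.

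This rests on reading both 75% and 82% as 2-year rates, on full follow-up of 36 to 42 men, and on assumed prevalences. The change is worth making because it is cheap and keeps the estimates finite. The MTD, the safety analyses and the Kaplan-Meier estimate of bPFS are unaffected.

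**What to change.** Replace the Cox clause in 10.4.3 with wording such as:

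> Associations of clinical variables with bPFS will be examined for exploration only. Covariates will be taken one at a time from a short list fixed before the analysis; continuous variables will be kept continuous. Firth-penalised Cox regression will be used, with profile-likelihood 95% confidence intervals. No multivariable model and no variable selection will be carried out.

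The investigators should choose the list; PSA at entry, interval since first radiotherapy and Gleason score are examples. Section 10.4.5 needs no edit.

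The cost is a wording change, and the method is available in standard software. What is given up is a multivariable model, which this number of events could not support. Penalisation keeps estimates finite when a category has no events; it does not make them precise, so the intervals should be reported with every hazard ratio.

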10.4.4 Safety Analyses

Adverse events will be coded as per the CTCAE v5.0. Each AE will be coded once for each patient based on the maximum severity during the assessment period. The relationship of AEs to study intervention will be recorded in addition to the onset date, end date, severity, expectedness, and outcome.

Dose-limiting toxicities will be defined as described in section [3.1.1](#).

10.4.5 Sub-Group Analyses

The primary endpoint is based on toxicity at a dose level. Only 3-6 patients will be included per dose level except for the expansion cohort. Thus, it is not feasible to include sub-group analyses.

10.4.6 Tabulation of individual Participant Data

Individual participant data may be tabulated for the exploratory endpoint of detecting mutational panel as a predictor of recurrence.

10.4.7 Exploratory Analyses

- Evaluate the feasibility of a patient specific circulating cell free DNA (cfDNA) mutation panel for predicting biochemical recurrence. We will first perform whole exome sequencing on the biopsy tissue acquired at baseline, and use that sequencing data to derive data on somatic mutations and somatic copy number alterations. We will also perform low-pass whole genome sequencing on total DNA extracted from plasma. Mutations detected in prostate biopsies harboring tumor that are not found in germline considered as potential contributors to each patient's individualized mutation panel. We will make direct comparisons whether a subset or all of the copy number alterations or mutations detected during baseline are represented in plasma prior to treatment. This will be reported as a binomial proportion (percent of patients with some or all of the panel detected and percent that have none of the panel detected). These same mutations defined from pretreatment

samples (evident in pretreatment plasma) will be evaluated in cfDNA (plasma) at each time point of follow up. Direct comparisons of whether a subset or all of the copy number alterations or mutations detected at baseline are represented in plasma will be performed and reported as a binomial proportion (percent of patients with some or all of the panel detected and percent that have none of the panel detected). We hypothesize that patients experiencing relapse will show mutations and copy number alterations present in cfDNA, versus responders where ctDNA would comprise a very small (if any) proportion of the total cfDNA. Because radiation may not kill cells immediately, but can result in late necrosis or mitotic catastrophe, it is not known what the optimal time point for analyzing a “nadir” in detectable mutations is or if one will be detected. Thus, this is an exploratory and descriptive project.

- Evaluate decision regret at the time of enrollment and at the end of follow up relating to the primary treatment for prostate cancer to determine if successful salvage mitigates decision regret. The percentage of patients scored as having decision regret will be compared to the percentage of patients not exhibiting decision regret (regarding the initial radiation treatment). It is hypothesized the effective salvage therapy will mitigate decision regret expressed at the time of enrollment.
- Evaluate for the presence of neuroendocrine markers in recurrent prostate cancer after prior irradiation. The number of cores and percentage of tumor on each core that stains positive for neuroendocrine markers (generally accepted measure is >1% of all cells) will be evaluated and reported in a descriptive fashion.
- Evaluate for the presence of markers of resistance in recurrent prostate cancer after prior irradiation. Additional markers of resistance may be queried in prostate tissue if tissue is available for analysis. These may include expression of immune markers, expression of brachyury, or expression of other proteins or transcripts implicated in radiation or therapeutic resistance.
- Describe cellular, molecular, genetic and genomic biology through whole exome or genome sequencing and targeted analysis in blood and tumor tissue.

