1.1.3 Exploratory Objectives

- Evaluate the feasibility of a patient specific circulating DNA mutation panel for predicting biochemical recurrence
- Evaluate decision regret at the time of enrollment and at the end of follow up relating to the primary treatment for prostate cancer to determine if successful salvage mitigates decision regret.
- Evaluate for the presence of neuroendocrine markers and markers of resistance in recurrent prostate cancer after prior irradiation.
- Describe cellular, molecular, genetic and genomic biology through whole exome or genome sequencing and targeted analysis in blood and tumor tissue.

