5.1.1 Plasma

Plasma will be sampled at baseline and every three months after SBRT

Three 8 mL aliquots of blood will be obtained in EDTA containing tubes, and one 8 mL aliquot of blood will be obtained in a Cell-Free DNA blood collection tube (BCT), such as Streck BCT. Following collection, tubes will be immediately placed on ice and transferred to the laboratory of [name] for processing and storage, [name], [contact]. The Cell-Free DNA BCT aliquot will be transferred to the laboratory of [name], [name], [contact].

Plasma will be stored and batched for analysis.

Plasma assays in [name] laboratory will include ELISA/Bioplex analysis of predictive biomarkers recently identified by the [name] laboratory that correlate with tumor resistance to radiotherapy (70 analytes). Studies in [name] laboratory will include germline DNA studies (baseline only) and circulating tumor DNA levels. Plasma studies in [name] laboratory will include surface receptor analysis by nanoFACS and RNAseq, for exosome and extracellular RNA analysis.

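### Section 10.4.7 reports the exploratory cfDNA result only as any versus none of the panel detected, which can hide the contrast of interest if responders often carry traces

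*Combined protocol and SAP*

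**What the plan says.** The objective in Section 1.1.3 is to "Evaluate the feasibility of a patient specific circulating DNA mutation panel for predicting biochemical recurrence".

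Section 10.4.7 builds each patient's panel from biopsy alterations that are absent from germline and looks for them in pretreatment plasma. At each follow-up time point it then tracks only those alterations already seen in pretreatment plasma. For both the baseline and the follow-up results, the only stated summary is this: "binomial proportion (percent of patients with some or all of the panel detected and percent that have none". In short, any part of the panel is set against no part of it.

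The hypothesis follows directly. For relapse it is worded as presence: "patients experiencing relapse will show mutations and copy number alterations present in cfDNA". For the comparison group the wording turns to amount: "versus responders where ctDNA would comprise a very small (if any) proportion of the total cfDNA". The paragraph closes: "Thus, this is an exploratory and descriptive project".

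Section 5.1.1 lists "germline DNA studies (baseline only) and circulating tumor DNA levels" among the plasma studies. No section says how those levels will be analysed, sets a positivity threshold, states a detection limit, or splits the reported proportion by relapse status. Section 10.4.6 permits a listing of individual data for this endpoint, but as an option and without mentioning levels.

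**The concern.** The contrast the hypothesis draws between the two groups is largely one of amount, because it leaves room for a responder to have a little ctDNA. The planned summary records only whether anything was found. Where small residues are present in many responders, the percent detected approaches its ceiling in both groups, and the summary no longer shows a difference that the levels would show.

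What is at stake is how far one exploratory objective can be interpreted. Few relapses are likely, so the information each patient contributes is worth keeping, and the finer measurement is already among the planned plasma studies.

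**Working it through.** The documents give no sample size, effect size, alpha, detection limit or power for the cfDNA analysis, so there is no stated figure to reproduce. The check is a reading of the text followed by two illustrations.

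**1. The categories, side by side (Section 10.4.7)**

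| Patient | Position under the hypothesis | Reported category |
|---|---|---|
| Responder, nothing found | very small or no ctDNA | none |
| Responder, one alteration at trace level | very small or no ctDNA | some or all |
| Relapser, whole panel at high level | alterations present | some or all |

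Rows two and three are on opposite sides of the hypothesis but share a category.

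**2. What the detected category tells the reader**

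Inputs: at most 42 evaluable patients (Section 10.2) and the 75% control rate cited in Section 10.1. Since 0.75 × 42 = 31.5, take 32 responders and 10 relapses. Section 10.1 gives the 75% no time point, so using it here is an assumption. Also assume that 90% of relapsers are detected (0.9 × 10 = 9) and that a fraction t of responders carry a detectable trace.

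Share of detected patients who relapsed = 9 / (9 + 32t)

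| t | Calculation | Share |
|---|---|---|
| 0% | 9 / 9 | 100% |
| 10% | 9 / 12.2 | 74% |
| 25% | 9 / 17 | 53% |
| 50% | 9 / 25 | 36% |
| 75% | 9 / 33 | 27% |
| 90% | 9 / 37.8 | 24% |

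The relapse share among all patients is 10 / 42 = 24%. At t = 90%, being detected says nothing about relapse. At t = 10% or less, the any/none cut works well.

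**3. How much a level would add**

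A simulation put log ctDNA levels on a normal scale, with relapsers 1.0 SD higher, and set the detection limit by the share of responders detected. It compared three two-sided 5% tests: Fisher's exact test on any/none, a rank test on the same any/none result (which removes Fisher's conservatism), and a rank test on the level with non-detects tied lowest. The shift and the detection shares are assumptions. Power for 10 relapses and 32 responders:

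| Responders detected | Any/none, Fisher | Any/none, rank test | Level, rank test |
|---|---|---|---|
| 20% | 54% | 59% | 66% |
| 30% | 50% | 59% | 71% |
| 50% | 40% | 51% | 72% |
| 70% | 19% | 27% | 74% |

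At 10% or less, with the same test on both scales, the difference is close to nil.

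**4. Allowing for the baseline restriction**

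Follow-up covers only alterations seen in pretreatment plasma, so a patient with none at baseline has nothing to track. If half the patients had a detectable baseline panel (an assumption: 5 relapses, 16 responders), power for Fisher on any/none versus the rank test on level is about 30% versus 39% at 20% responder detection, and 18% versus 41% at 50%. The level still carries more information, but neither scale would support firm inference at that shift.

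**The case against.** The strongest reply is that the plan contains no between-group test. It calls the work descriptive, states a feasibility aim, and does not split the proportion by relapse status. Power lost by an unplanned test is not a flaw in the plan, and the missing link to relapse is arguably the larger gap. That stands: the power figures above only illustrate lost information. It does not remove the point, because a descriptive summary should still be able to show the pattern its own hypothesis describes.

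A second reply is that levels are not thrown away: Section 5.1.1 plans them and Section 10.4.6 allows individual listings. This is fair mitigation, but the listing is optional and does not name levels.

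Some stronger readings are tempting. A reader might infer that the plan expects most responders to be positive because it mentions delayed cell death after radiation. Section 10.4.7 says only that killing may not be immediate and that the timing of any low point is unknown; its hypothesis for responders includes zero. Responder detection of 50–70% therefore has no support in the documents. A reader might also take 10 relapses as a ceiling or an expectation. Section 1.2.5 reports no recurrence at Arm 1 dose level 1 and none in five treated Arm 2 patients, so the number could be much lower; nothing in the documents caps it either.

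**Conclusion.** The point holds as a limited one. Any/none is the only summary stated for the cfDNA result, and it can hide a difference in amount that the hypothesis allows for. The loss ranges from close to nil, if 10% or fewer of responders carry a detectable trace, to most of the contrast, if about 70% or more do. The documents do not give that rate, the assay detection limit, or the number of relapses among patients with a baseline-detectable panel, so no single size can be stated.

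It would go too far to say that the trial will wrongly report no difference, since no comparison is planned. It would also go too far to call the hypothesis purely quantitative: its relapse half is worded as presence, and the wording about amount is on the responder side. The MTD and safety conclusions are not affected. This is an inexpensive improvement to an exploratory analysis.

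**What to change.** In Section 10.4.7, define the follow-up denominator as patients with a panel evident in pretreatment plasma. For them, report per patient and visit, in addition to any/none:

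- the share of panel alterations detected; and
- the ctDNA level planned in Section 5.1.1, in whatever quantitative unit the assay yields, with non-detects tied at the lowest rank.

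Summarise both descriptively by visit and by relapse status. If the groups are contrasted, use a rank-based measure such as the AUC with a confidence interval. Keep the any/none proportion as a supportive summary.

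The cost is analysis wording and a modest amount of programming, using measurements already planned. The documents do not say what unit the assay gives, so the wording should not presume tumour fraction or variant allele fraction. The downsides are that levels just above the detection limit are noisy, which tying the non-detects does not cure, and that estimates will be imprecise with few relapses.

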- PROMIS – Depression SF4a: The PROMIS Depression item bank assesses self-reported negative mood (sadness, guilt), views of self (self-criticism, worthlessness), and social cognition (loneliness, interpersonal alienation), as well as decreased positive affect and engagement (loss of interest, meaning, and purpose). The depression short forms are universal rather than disease-specific. All assess depression over the past seven days. PROMIS instruments are scored using item-level calibrations.
- PROMIS – Anxiety SF4a: The PROMIS Anxiety item banks assess self-reported fear (fearfulness, panic), anxious misery (worry, dread), hyperarousal (tension, nervousness, restlessness), and somatic symptoms related to arousal (racing heart, dizziness). Anxiety is best differentiated by symptoms that reflect autonomic arousal and experience of threat. Only one behavioral avoidance item is included in the adult item bank; therefore, behavioral fear avoidance is not fully evaluated. The anxiety measures are universal rather than disease-specific. All assess anxiety over the past seven days.

- PROMIS – Psychosocial Impact Positive SF 4a assess positive psychosocial (emotional and social) outcomes of illness, previously conceptualized in various ways including post-traumatic growth, benefit-finding, and meaning making. Positive Illness Impact refers to positive psychosocial outcomes of illness that can occur as a result of confrontation with one's mortality, such as greater life appreciation, interpersonal relationships and personal resources.
- Decision Regret Scale (DRS) is a 5-item scale measuring distress or remorse after a health case decision. It has been psychometrically validated in the prostate cancer population. The score correlated with satisfaction with the decision ($r=-0.40$ to -0.60), decisional conflict ($r=0.31$ to 0.52), and overall rated quality of life ($r=-0.25$ to -0.27).

Once data is abstracted, questionnaires will be maintained in the research chart (print or electronic). If stored, electronically, these files will have restricted access and be accessible only to members of the study team. In the event that questionnaires are stored electronically, paper copies will be shredded.

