10 STATISTICAL CONSIDERATIONS

This is a single-institution, two-arm, Phase I trial, where patients with locally recurrent prostate cancer after prior radiotherapy will receive image-guided, focally dose escalated SBRT to the sites of local recurrence. Patients will be treated with escalated doses of radiation with the escalation on each arm occurring in parallel, and inclusion on each arm based on prior radiation treatment received. The primary endpoints will be to define the MTD of this approach. The secondary endpoints include to define DLTs, to describe the rate of 1 and 2-year biochemical relapse free survival (Phoenix criteria), to evaluate DCFPyL imaging as a method to detect locally recurrent prostate cancer after irradiation, and to define the quality of life changes that occur during and after this treatment. Exploratory endpoints include description of decision regret in patients who failed treatment and are successfully or unsuccessfully salvaged, evaluation of a personalized mutation panel for detection of early recurrence, and evaluation for the presence of neuroendocrine markers and markers of resistance in radio-recurrent prostate cancer.

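### The decision-regret analysis in 10.4.7 compares two complementary percentages from an undefined yes/no split of the DRS, so it estimates neither change from enrolment nor a difference by salvage outcome

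*Combined protocol and SAP*

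**What the plan says.** Section 10.4.7 states the objective: "Evaluate decision regret at the time of enrollment and at the end of follow up relating to the primary treatment for prostate cancer", in order to learn whether successful salvage lessens regret. The analysis follows: "The percentage of patients scored as having decision regret" is to be set against the percentage without it, with a note that the regret concerns the initial radiation. The expected direction is then given: "It is hypothesized the effective salvage therapy will mitigate decision regret expressed at the time of enrollment". No test, model, cut point or comparison group is named.

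Other sections bear on this:

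- Section 10 summarises the same endpoint as "description of decision regret in patients who failed treatment and are successfully or unsuccessfully salvaged", which points to a contrast by salvage outcome.
- Section 3.4 introduces the instrument: "Decision Regret Scale (DRS) is a 5-item scale measuring distress or remorse after a health case decision". Its validity is described through correlations of the score.
- The study calendar (3.6) collects the DRS at baseline and in every post-therapy follow-up column. Section 6.1.1 lists questionnaire scores among the data captured.
- Section 10.4.3 fits a linear mixed model to patient-reported scores, but that bullet names only SHIM, the AUA Symptom Index and EPIC-26.
- Section 10.2 allows at most 42 evaluable patients.
- Appendix B says the questionnaires are kept in a separate manual, which is not part of these documents.

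**The concern.** There are two faults in one sentence, and the first is the larger.

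The share with regret and the share without are a single number, p and 1 − p. Comparing them asks whether p differs from one half at whatever time it is measured. The objective is about movement in regret between two times, and about whether that movement depends on the success of salvage. The stated comparison speaks to neither, and supplying a cut point would not change that.

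Second, a multi-item score is reduced to yes or no with no rule for the split. A patient whose regret falls a long way on one side of the cut counts as unchanged, while a small shift across it counts as full mitigation. Without a stated cut, nothing in these documents prevents the definition from being settled after the data are seen. The same section does give a threshold for neuroendocrine staining (more than 1% of cells), so the omission falls short of the plan's own practice.

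At stake is whether this objective can be answered from a small sample whose full scores will already be in the database.

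**Working it through.** The plan gives no sample size, alpha, power or effect size for decision regret, so there is no figure of its own to reproduce. The documents supply the instrument (5 items), the two time points and the maximum of 42 evaluable patients. Everything else below is assumed and shown as a range.

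**1. The stated comparison.** The difference is p − (1 − p) = 2p − 1. Suppose p = 20% at enrolment: the difference is 20 − 80 = −60 points. If p is again 20% at the end of follow-up, it is again −60 points although nothing changed. If p falls to 10%, it is −80 points, and neither figure alone is the 10-point fall. Salvage outcome does not enter.

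**2. Information kept by a yes/no split.** For a normal score with share p above cut c, the efficiency relative to the full score at one time point is E = φ(c)² / [p(1 − p)]. For a paired change it is E × (1 − ρ)/(1 − r), where ρ is the correlation of the two scores and r that of the two yes/no values.

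- Worked case, p = 50%, ρ = 0.5: E = 0.3989²/0.25 = 0.637; r = 0.333; kept = 0.637 × 0.5/0.667 = 0.48.
- Worked case, p = 20%, ρ = 0.5: E = 0.2800²/0.16 = 0.490; r = 0.295; kept = 0.490 × 0.5/0.705 = 0.35.

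| Share with regret | kept, ρ = 0 | ρ = 0.3 | ρ = 0.5 | ρ = 0.8 |
|---|---|---|---|---|
| 50% | 64% | 55% | 48% | 31% |
| 30% | 58% | 49% | 42% | 27% |
| 20% | 49% | 41% | 35% | 22% |
| 10% | 34% | 28% | 23% | 14% |

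The loss runs from 36% (median cut, ρ = 0) to 78% (20% with regret, ρ = 0.8), and to 86% in the extreme corner. A simulated skewed 5-item score with five levels per item (number of levels assumed) and correlation near 0.5 kept 8% to 51%. The 8% came from a cut that classed 98% of patients as regretful.

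**3. Power for before/after change, n = 42.** Assumptions: ρ = 0.5, two-sided 5%, paired t on the score against mid-p McNemar on the split, 20/35/50% with regret at baseline, about 10% of patients at the scale's floor. Simulated:

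| True fall | Full score | Yes/no (20/35/50%) |
|---|---|---|
| 0.3 SD | 44% | 15 / 22 / 25% |
| 0.4 SD | 67% | 24 / 32 / 39% |
| 0.5 SD | 86% | 34 / 49 / 55% |

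The floor matters. With half the patients at the floor at baseline, full-score power drops to about 30%, 45% and 61%. The yes/no figures hardly move, so the gain shrinks to about 6 to 30 points, within a point or two of simulation error.

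**4. Power for the salvage contrast.** Section 10.1 quotes a 75% control rate for brachytherapy, and section 1.2.1 reports 82% two-year bPFS in the earlier SBRT series. These give 42 × 0.25 = 10.5 and 42 × 0.18 = 7.6 failures, about 8 to 10. At ρ = 0.5 the SD of change is √[2(1 − 0.5)] = 1 SD, so the noncentrality is d/√(1/n₁ + 1/n₂).

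- 8 vs 34, d = 0.3: 0.3/0.393 = 0.76, power about 12%.
- 10 vs 32, d = 0.5: 0.5/0.362 = 1.38, power about 27%. With 11 vs 31 it is about 28%.

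**The case against.** The strongest reply is about weight. This is one of several exploratory objectives in a phase I trial whose primary endpoint is the MTD, and no decision depends on it. The scores are captured, so nothing is lost from the data, and the full-scale analysis could be done later anyway. The separate questionnaire manual may hold a scoring rule. All of this stands, and it keeps the point minor. It does not repair the sentence, because a cut in a manual would still leave two complementary percentages being compared.

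It can also be said that the intended analysis is plain from the objective: compare the percentage at enrolment with that at the end. That is a reasonable guess, but section 10 suggests a different contrast, by salvage outcome, and 10.4.7 states neither.

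Three stronger readings are tempting and are not supported:

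- **That the split discards most of the information.** It does so under the normal model once the correlation is about 0.45 or more, or when 20% or fewer have regret. With a low correlation and a cut near the median the loss is 36-48%. The documents give no prevalence, SD or correlation.
- **That using the full score would make the objective well powered.** The gains in step 3 concern a one-group before/after change, and the McNemar test there is an assumption, since the plan names no test. For the salvage contrast, power is low on any scale.
- **That the cut will be chosen after the data are seen.** The documents leave this open, but they do not show it.

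**Conclusion.** The point holds as a minor one. On the text alone, the stated comparison answers neither part of the objective, and no cut point is given. The cost of dichotomising is roughly one third to four fifths of the information on within-patient change, conditional on the assumed cut, correlation and floor. The gain in power for before/after change could be large or small: 19 to 52 points in the n = 42 scenarios with few patients at the floor (44 − 25 = 19; 86 − 34 = 52), and about 6 to 30 with half of them there. For the difference by salvage outcome, about 8 to 10 failures among 42 patients leave power near 12-28% for differences of 0.3-0.5 SD even with the full score, so that result can only be descriptive.

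**What to change.** In 10.4.7, replace the percentage comparison with an analysis of the total DRS score:

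- Use the mixed-model approach of 10.4.3, with time, biochemical control status (as defined in 6.3.2) and a status-by-time term. The interaction is needed because status as a main effect alone does not show whether the change differs by salvage outcome.
- Report the within-patient change from enrolment to end of follow-up with a 95% CI.
- Report the difference in that change between successfully and unsuccessfully salvaged patients with a 95% CI, labelled descriptive.
- If a yes/no percentage is also wanted, show it at both time points as supportive, with the cut fixed before analysis and its source cited. If the questionnaire manual already holds a scoring rule, refer to it.

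The cost is a sentence or two in 10.4.7. No new data, visits or patients are needed, and the percentage can still be reported.
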